## 1 STATISTICAL CONSIDERATIONS

### 1.1 STATISTICAL HYPOTHESES

Primary Endpoint: We hypothesize that at least 60% of eligible patients approached will enroll in the TRAC-AYA study.

### 1.2 SAMPLE SIZE DETERMINATION

The sample size of 40 is based on the goal of estimating the probabilities and means for 3 feasibility outcome measures (enrollment  $\geq$  60% [primary], retention  $\geq$  60%, adherence [defined as  $\geq$ 70% completing at least 60% of sessions]). Assuming a negative binomial distribution and true probability of enrollment of 60%, the probability that we would have to approach 55 or more people to recruit 40 is  $<0.05$ . If we approach  $\geq$ 55 AYAs to enroll 40, it is unlikely the true probability of enrollment is 60% or greater, concluding a future efficacy study may not be feasible. Out of 40 AYAs, if the true probability of retention is 60% we expect at least 19 AYAs will be retained (i.e., probability of  $n \leq 19$  retained given true retention probability of 60% is  $<0.05$ ), so if more than 21 AYAs are not retained, an efficacy study may not be feasible. We have 80% power (using a 2-tailed alpha of 0.05) to detect an adherence proportion of 0.72 if we assume a null hypothesis adherence proportion of 0.50.

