- 5) meeting hazardous drinking criteria on the AUDIT-C questionnaire, defined as a score of 3 or higher for women/4 or higher for men (The AUDIT-C consists of items 1, 2, and 3 from the full AUDIT questionnaire);

Participants with severe psychopathology (psychosis, suicidal behavior, substance dependence) will be excluded from the study. The AUDIT questionnaire will be administered as part of screening to determine alcohol dependence; if survivors have a score of 20 or higher, they will be referred to UKMCC Social Work.

**RCT:** n=50, Intervention group (TRAC) n=25, and Control group (education and monitoring) n= 25. To be eligible to participate in the RCT, survivors must meet the following criteria:

- 1) diagnosed with cancer between age 15-39;
- 2) currently age 18-39;
- 3) 3 months - 15 years posttreatment (hormonal therapy allowed);
- 4) report unhealthy alcohol use in the previous 3 months, defined as:
  - a. exceeding moderate daily drinking levels (more than 1 drink/day for women, more than 2 drinks/day for men) at least 3 times in the past 3 months OR
  - b. engaging in heavy weekly drinking (more than 7 drinks/week for women, more than 14 drinks/week for men) at least once in the past 3 months OR
  - c. engaging in binge drinking (more than 3 drinks/sitting for women, more than 4 drinks/sitting for men) at least once in the past 3 months; OR
- 5) meeting hazardous drinking criteria on the AUDIT-C questionnaire, defined as a score of 3 or higher for women/4 or higher for men (The AUDIT-C consists of items 1, 2, and 3 from the full AUDIT questionnaire)
- 5) Reside in the United States

Just as with the Open Pilot, participants with severe psychopathology will be excluded from the study. The AUDIT questionnaire will be administered as part of screening to determine alcohol dependence; if survivors have a score of 20 or higher, they will be referred to UKMCC Social Work (if a patient at UK HealthCare). Non-UK patients will be provided with information for SAMHSA's treatment finder, national helpline, and local resources based on the zip code provided at the time of screening. Survivors who score a 20 or higher on the AUDIT questionnaire will not be eligible for the study, as this study is not designed to manage alcohol dependence and its immediate health risks.

Enrollment will begin February 2022 and continue through May 2023 or until the proposed participant pool is reached.

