## Objectives

List your research objectives. Please include a summary of intended research objectives in the box below.

Posttreatment rural AYAs are an underserved group at risk for increased alcohol use and poor access to interventions, ultimately leading to poorer physical and mental health. mHealth interventions are recommended for AYAs and have shown high acceptability and positive health effects. To address the lack of mHealth interventions for alcohol use among rural AYAs, we will adapt and pilot an existing mHealth intervention (TRAC) to reduce alcohol use. We will conduct the study in Kentucky, which leads the nation in cancer incidence and mortality, has a higher incidence of AYA cancers compared to other states, is 40% rural, and encompasses over 100 medically underserved areas. The study team has expertise in mHealth interventions, cancer survivorship, clinical trials, and AYA oncology. Thus, we are well-equipped to complete the following Aims:

1. Adapt and refine TRAC for rural posttreatment AYAs. We will conduct semi-structured interviews with key informants (N=14; 6 AYAs, 8 AYA oncology clinicians and community advocates), and conduct an open pilot study (i.e., fully implement the intervention) with a small number of patients (N=4; 2 TRAC, 2 control comparison) to adapt the content and delivery procedures of TRAC for rural AYA cancer survivors, resulting in TRAC-AYA.

2. Test the feasibility and acceptability of conducting an RCT of TRAC-AYA with AYAs (N=50; 25 TRAC, 25 control comparison). Comparison group will receive alcohol monitoring and educational materials. The primary feasibility outcome will be enrollment (=60% of eligible AYAs approached enroll). Secondary feasibility outcomes include retention (=60% complete follow-up) and intervention adherence (=70% complete =60% of intervention sessions; alcohol monitoring =70%). Acceptability will be assessed with mean ratings (scores =7 out of 10) of intervention relevance, helpfulness, and convenience. We will also obtain preliminary data on alcohol use frequency, quantity, binge drinking, and health (PROMIS-29).

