#### Study Procedures: Randomized Controlled Trial

To achieve Aim 2, we will conduct a pilot RCT of the TRAC-AYA intervention with a total of 50 participants (25 per condition).

Participants in the RCT will be enrolled in the study for a total of 10 weeks, whether they are in the intervention or control group. If participants are unable to complete monitoring or intervention tasks within the initial 4-week period, they will be given up to 6 weeks to complete the tasks before being considered noncompleters. The delayed post-test is delivered 4 weeks after completion of all monitoring/intervention tasks at 10 weeks.

Intervention (Group A) participants will complete 4 intervention sessions on a weekly basis, conducted via phone or videoconference (HIPAA-compliant Zoom), according to participant preference. These sessions will be audio recorded. Participants will also complete daily self-monitoring of alcohol use using mobile surveys and breathalyzers for 6 weeks. Control (Group B) participants will receive educational materials regarding alcohol use and will complete mobile monitoring of alcohol use in the same manner as Group A for 6 weeks. All RCT participants will complete a baseline assessment survey upon enrollment, a follow-up survey once all intervention/monitoring tasks are completed at 6 weeks, and a qualitative exit interview which will be audio recorded. All RCT participants will also complete a delayed post-test assessment at 10 weeks, 4 weeks after they complete the follow-up survey.

The total estimated maximum time commitment for RCT Group A (Intervention) participants is 13 hours, 45 minutes. The total estimated maximum time commitment for RCT Group B (Control) participants is 10 hours, 45 minutes.

All RCT participants will receive up to \$315 in Amazon e-gift cards for their participation.

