**RCT Enrollment:** The RCT will enroll 50 participants, 25 per condition. First, we will administer a screener to verify participants meet all inclusion criteria. If patients do not wish to be screened and are not interested in participating in the study, we will ask that they complete a brief Refusal to Screen Questionnaire to indicate why and collect basic demographic information to inform generalizability of the obtained sample. If participants complete the screener and indicate that they are interested in learning more about the study, we will collect their contact information and a member of the study team will follow-up with the participant to obtain informed consent and complete enrollment if they meet all eligibility criteria. Pre-screened participants who screen eligible and indicate interest in the study will be automatically directed to the approved eConsent in REDCap. If participants are determined to be eligible for the study and

consent to enroll, we will also collect information for at least 1 emergency contact (participants have the option to provide a backup emergency contact). We will contact these individuals only in cases of extreme distress, adverse events, or threats of self-harm. We will make clear to participants that we will not specify the nature of the research study to these individuals. If the participant is a patient at UK HealthCare, researchers will also contact their medical care team should any of these cases arise. Once participants have been enrolled in the study they will complete a baseline questionnaire, which may be done in-person, online via REDCap, via phone, or via mail per participant preference. It will ask about 1) Alcohol use, consequences, and attitudes, 2) Tobacco and other substance use, 3) Cancer history, 4) Overall physical/mental health, 5) Healthcare usage and history, 6) Financial toxicity, 7) Health literacy, 8) Coping Self-efficacy, 9) Social support, and 10) Drinking refusal self-efficacy.

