### 1.3 POPULATIONS FOR ANALYSES

The sample from Aim 1 ( $n = 18$ ) will be used to refine procedures and the intervention protocol. The sample from Aim 2 ( $n = 40$ ) will be used to analyze feasibility and acceptability data and describe pre-post changes in patient-reported outcomes.

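### SAP section 1.2 is written for 40 participants when the protocol randomizes 50, and its primary enrollment cut-off of 55 lies on the wrong tail

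*Combined protocol and SAP*

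**What the plan says.** **Sample size in the SAP.** Section 1.2 opens with "The sample size of 40 is based on the goal of estimating the probabilities and means for 3 feasibility outcome measures". Section 1.3 repeats the number: "The sample from Aim 2 ( $n = 40$ ) will be used to analyze feasibility and acceptability data".

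**Sample size in the protocol.** Four places give 50:
- Study Population: "n=50, Intervention group (TRAC) n=25, and Control group (education and monitoring) n= 25"
- Objectives, Aim 2: "Test the feasibility and acceptability of conducting an RCT of TRAC-AYA with AYAs (N=50; 25 TRAC, 25 control comparison"
- Study Procedures: Randomized Controlled Trial: "we will conduct a pilot RCT of the TRAC-AYA intervention with a total of 50 participants (25 per condition"
- Data Collection & Research Materials: "The RCT will enroll 50 participants, 25 per condition"

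**Decision counts in SAP 1.2.** All are tied to 40.
- *Enrollment (primary).* With a negative binomial model and a true rate of 60%, the SAP says "the probability that we would have to approach 55 or more people to recruit 40 is" below 0.05. It concludes that reaching 55 makes a true rate of 60% or more unlikely, so an efficacy study may not be feasible.
- *Retention.* At a true 60%, at least 19 of 40 are expected to be retained. A parenthesis puts the probability of 19 or fewer below 0.05, and the rule flags the study if more than 21 are lost.
- *Adherence.* 80% power is claimed for 0.72 against a null of 0.50, two-sided alpha 0.05.

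On who receives sessions, the protocol says "Intervention (Group A) participants will complete 4 intervention sessions on a weekly basis". The control arm receives educational materials and monitoring.

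**The concern.** The SAP speaks of recruiting and enrolling 40, and the protocol of enrolling 50. These are two enrollment targets; 40 is nowhere described as an evaluable subset or an expected number of completers. A rule written as a count is valid only for the sample size behind it, so the planned trial has no stated count rule for enrollment or retention.

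The enrollment rule also looks wrong without any exact calculation. At 60%, enrolling 40 takes 40/0.6 = 66.7 approaches on average. Stopping at 55 means 40/55 = 72.7%, which is better than the target, yet the SAP reads it as a sign of infeasibility.

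The stake is the pilot's main output. Enrollment is the primary endpoint, and the protocol says the feasibility data are to inform a definitive RCT. Under the rule as written, a trial that approaches 60 to enroll 40 (66.7%) meets the 60% target and is also flagged as possibly infeasible.

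**Working it through.** **Inputs.** From SAP 1.2: target rate 0.60 for enrollment and retention; 40 enrolled; cut-offs of 55 approached, 19 retained and 21 lost; adherence 0.72 against 0.50, two-sided alpha 0.05. From the protocol: 50 enrolled, 25 per arm.

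**1. Enrollment, the SAP's own figure.** Let T be the number approached to enroll r. Then P(T ≥ m) = P(Bin(m−1, 0.6) ≤ r−1) and P(T ≤ m) = P(Bin(m, 0.6) ≥ r).
- r = 40: P(T ≥ 55) = P(Bin(54, 0.6) ≤ 39) = 0.978. The stated value below 0.05 does not reproduce.
- P(T ≤ 55) = 0.035 and P(T ≤ 56) = 0.052, so 55 is the 5% point of the opposite (fast-enrollment) tail.
- Reading 55 as the number of refusals gives 0.0002, so that reading does not explain the cut-off either.
- At a true rate of 70%, the rule as written still flags with probability 0.688.

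**2. Enrollment, correct upper-tail cut-offs.**

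| Enrolled | Mean approached | One lower | Smallest m with P(T ≥ m) < 0.05 |
|---|---|---|---|
| 40 | 40/0.6 = 66.7 | 78: 0.061 | 79: 0.047 |
| 50 | 50/0.6 = 83.3 | 96: 0.059 | 97: 0.047 |

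With r = 50, P(T ≥ 55) exceeds 0.9999. Of the move from 55 to 97, 79 − 55 = 24 is the tail error and 97 − 79 = 18 is the change in sample size.

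**3. Retention**, X ~ Bin(n, 0.6).
- n = 40: P(X ≤ 19) = 0.074, so the parenthesis is wrong. P(X ≤ 18) = 0.039. More than 21 lost means 18 or fewer retained, so the operative rule is valid at 40.
- n = 50: P(X ≤ 23) = 0.031 and P(X ≤ 24) = 0.057, so the flag is 23 or fewer retained, i.e. 27 or more lost.
- If the counts for 40 were carried over to 50 (hypothetical): more than 21 lost means 28 or fewer retained, probability 0.330; fewer than 19 retained has probability 0.0005. The intended rate is below 0.05.

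**4. Adherence**, exact equal-tailed two-sided binomial test of 0.50, true value 0.72.

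| n | Rejects high at | Power |
|---|---|---|
| 40 | ≥ 27 | 0.794 |
| 25 | ≥ 18 | 0.600 |
| 20 | ≥ 15 | 0.495 |

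The claimed 80% reproduces at 40 (0.794 exact, 0.820 by normal approximation). With 25, power reaches 80% at a true proportion of about 0.77 (0.801).

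**5. Subject totals.** The demographics table sums to 4+2+6+8+5+4+25+49 = 103, which equals 14+4+50+35 (first interviews, open pilot, RCT, added interviews). The stated maximum of 94 lies below 103; with an RCT of 40 the sum is 14+4+40+35 = 93.

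**The case against.** The strongest reply is that nothing essential depends on these counts. The 60% criteria do not depend on sample size. SAP 1.4.2.1, the analysis section, plans 95% confidence intervals and tests against the hypothesized values, which work at any size. The counts sit in a sample-size section and are softly worded. This stands as far as estimation goes: the estimates and intervals are unaffected. It does not rescue the counts, which are the only place where the SAP says what result would argue against a future trial. For the primary endpoint that statement points the wrong way.

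Four narrower points have force.
- The retention slip is minor, because the operative rule is right at 40. The carry-over figures describe a misuse that no document prescribes.
- Fixed replacement counts are safe only if the final number is 40 or 50. The protocol says enrollment is closed but does not give the number enrolled.
- A one-sided 5% cut-off and the 60% criterion can disagree. Enrolling 50 of 90 gives 55.6%, which misses the target but is not flagged by a cut-off of 97. With online advertising and referral recruitment, who counts as approached also needs care.
- SAP 1.4.2.1 lists alcohol monitoring under adherence, and both arms do that, so 25 is the denominator for sessions only. SAP 1.2 defines session adherence as 60% of sessions and 1.4.2.1 as 75%. With four sessions both mean at least three (0.60 × 4 = 2.4; 0.75 × 4 = 3), so this does not alter the power calculation.

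**Conclusion.** The concern holds and must be fixed. The inverted enrollment rule is the most serious part. It is wrong at either sample size, and replacing 40 by 50 does not cure it. The conflict over sample size is real and unreconciled, and it leaves the count rules undefined for the planned trial. The retention parenthesis is a small correction. The adherence power is right for 40 people and overstated for the people who actually receive sessions.

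These results rest on the SAP's own assumptions: independent approaches and participants, a true rate of exactly 60% for enrollment and retention, and a one-sided 5% flag. The adherence figure of 0.60 further assumes the 25 intervention participants as the denominator and an exact test.

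**What to change.** 1. **Reconcile the sample size** across SAP 1.2, SAP 1.3 and the protocol, and check the stated maximum of 94 subjects against the demographics total of 103.
2. **Enrollment.** State that 55 was taken from the wrong tail. Replace it with 97 or more approached to enroll 50 (0.047), or 79 or more if 40 is kept (0.047). Give the formula as well, so that it can be applied to the number actually enrolled. Define who counts as an eligible person approached, and say whether the 60% criterion or the count governs when they disagree.
3. **Retention.** For 50, flag at 23 or fewer retained, i.e. 27 or more lost (0.031). For 40, keep the rule and correct the parenthesis to 18 or fewer (0.039).
4. **Adherence.** State the denominator separately for sessions and for monitoring. For sessions on 25 participants, report power of about 60% for 0.72 against 0.50, with 80% reached at about 0.77. Align the 60% and 75% session definitions.

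**Cost.** No extra participants or data are needed. Because enrollment has closed, the change alters decision rules after the fact. It should be a dated SAP correction with its rationale and a statement of whether feasibility data had already been seen. The session-adherence power claim falls from 80% to about 60%.

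### The primary enrollment rule uses the wrong tail: at 60% true enrollment, approaching 55 or more to enroll 40 has probability 0.98, not below 0.05, so a feasible trial would almost surely be flagged infeasible

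*Combined protocol and SAP*

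**What the plan says.** SAP section 1.1 gives the primary hypothesis: "We hypothesize that at least 60% of eligible patients approached will enroll in the TRAC-AYA study". Section 1.4.2.1 defines the measure as the number enrolled divided by the number of eligible AYAs approached.

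Section 1.2 turns this into a decision rule. "Assuming a negative binomial distribution and true probability of enrollment of 60"%, it says that "the probability that we would have to approach 55 or more people to recruit 40 is" less than 0.05. It then concludes that with 55 or more approached "it is unlikely the true probability of enrollment is 60% or greater, concluding a future efficacy study may not be feasible".

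The rule is tied to 40 enrollees, which sections 1.2 and 1.3 both use. The protocol has a different target: under Study Procedures: Randomized Controlled Trial, "we will conduct a pilot RCT of the TRAC-AYA intervention with a total of 50 participants (25 per condition").

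**The concern.** Anyone enrolling at 60% needs on average about 67 approaches to reach 40, so needing at least 55 is the normal course of events. A rule that treats it as a less-than-5% event points the wrong way.

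Enrollment is the sole primary endpoint, and the protocol's Objectives section says the study's feasibility data will inform a definitive trial. With the tail reversed, a pilot that exactly meets its hypothesis would be reported as casting doubt on the next trial. The SAP would also contradict itself: 40 enrolled from 66 approached is 60.6%, which satisfies section 1.1 and is flagged by section 1.2.

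**Working it through.** **Inputs, all from SAP section 1.2:** true enrollment probability p = 0.60; negative binomial model; r = 40 to enroll; cutoff 55 approached; stated probability below 0.05. For sensitivity, r = 50 from the protocol's RCT procedures.

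**Formula.** Let N be the number approached when the r-th person enrolls. At least n approaches are needed exactly when the first n − 1 give at most r − 1 enrollees:

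- P(N ≥ n) = P(Bin(n − 1, p) ≤ r − 1)
- P(N ≤ n) = P(Bin(n, p) ≥ r)

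**Step 1: try to reproduce the stated figure.**

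- Mean of N = 40/0.60 = 66.7; SD = √(40 × 0.40)/0.60 = 6.7. The cutoff of 55 lies about 1.75 SD below the mean: (66.7 − 55)/6.7.
- P(N ≥ 55) = P(Bin(54, 0.60) ≤ 39) = **0.978**. The SAP states less than 0.05.

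**Step 2: other readings of the upper tail.**

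| Reading | Probability |
|---|---|
| Normal approximation, with or without continuity correction | 0.966 or 0.960 |
| Success and failure swapped (p = 0.40) | about 1.00 |
| 50 enrollees in place of 40 | about 1.00 |
| 55 refusals in place of 55 approached | 0.0002 |

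Only the last falls below 0.05. It contradicts the SAP's wording, which counts people approached, and 55 is not the 5% point on that scale either. That point is 39 refusals, i.e. 39 + 40 = 79 approached.

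**Step 3: where 55 comes from.** P(N ≤ 55) = 0.035 and P(N ≤ 56) = 0.052. So 55 is the largest n whose *lower* tail is below 0.05, which identifies the error as a tail reversal. In observed terms, 40/55 = 72.7%.

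**Step 4: operating characteristics as written (r = 40, flag at 55 or more).**

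| True enrollment | P(flagged infeasible) |
|---|---|
| 60% | 97.8% |
| 65% | 89.7% |
| 70% | 68.8% |
| 75% | 36.8% |
| 80% | 10.7% |
| 82% | 5.1% |

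The flag rate comes down to about 5% only when true enrollment is about 82%. If 50 were enrolled and 55 kept, the flag rate would exceed 99.99% at 60% and be 99.0% at 80%. No section pairs 50 with 55, so this is only a warning against carrying the number over.

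**Step 5: the cutoff that meets the stated aim at p = 0.60.**

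| Enrolled | Smallest n with P(N ≥ n) < 0.05 | P(N ≥ n) | P at n − 1 | P(flagged) at true 50% |
|---|---|---|---|---|
| 40 | 79 | 0.0468 | 0.0606 | 55% |
| 50 | 97 | 0.0467 | 0.0591 | 62% |

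**The case against.** The arithmetic cannot be defended. The case on the other side concerns consequence and remedy.

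- **The wording is advisory.** Section 1.2 says a future trial may not be feasible, not that it is ruled out. That is true, but the advice still rests on a false probability and points the wrong way.
- **Section 1.4.2.1 has a sound analysis.** It plans the enrollment proportion, 95% confidence intervals and tests against 60%. For 40 of 66 the exact interval is about 48% to 72%, compatible with the target. So the 97.8% applies when the section 1.2 cutoff is used mechanically. This stands as a limit on the practical damage. It does not remove the rule: the SAP would hold two opposite readings of the same data, with nothing to say which governs.
- **The figures for 50 enrollees are hypothetical.** Agreed. The 40-versus-50 discrepancy is a separate matter, and the finding holds in full with 40 alone.
- **The corrected cutoff has its own weakness.** Under the 79 rule, 40 enrolled from 78 approached is 40/78 = 51%, and it would not be flagged although the stated criterion is 60%. This stands. It follows from asking for strong evidence against 60% with a sample this small, and it should be disclosed.

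**Conclusion.** The concern holds as stated. Under the SAP's own model, the probability given as below 0.05 is 0.978, and the inference drawn from it is reversed. At a true rate of exactly 60%, the rule flags infeasibility in about 98 of 100 such trials, against an intended fewer than 5. The error shrinks as true enrollment rises, to 36.8% at 75% and 10.7% at 80%.

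This rests only on the figures in section 1.2 and on the negative binomial assumption of independent approaches with a common enrollment probability. It needs no outside figure. It affects the feasibility conclusion, not the treatment or safety of any participant. It must be corrected because it governs the reading of the only primary endpoint.

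**What to change.** In SAP section 1.2, replace the cutoff and its probability with the correct upper tail, matched to the enrollment target once 40 and 50 are reconciled:

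- 50 enrolled: flag if 97 or more eligible AYAs are approached (P = 0.047 at 60%).
- 40 enrolled: flag if 79 or more are approached (P = 0.047 at 60%).

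State the operating characteristics beside the rule. At a true 50% it flags 62% of the time with 50 enrolled and 55% with 40, so an unflagged result is not evidence that enrollment reached 60%. Say in section 1.4.2.1 that the 95% interval for enrollment will be exact, report it next to the rule every time, and state how the rule and the interval are read together.

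The cost is SAP wording only, with no extra data or participants. The protocol's Informed Consent Process section says the study is closed to enrollment, so the number approached may already be known. The change should therefore be entered as a dated correction of an arithmetic error, noting that the new cutoff depends only on the 60% hypothesis and the enrollment target, not on observed data.

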#### 1.4.2 AIM 2 ANALYSES

##### 1.4.2.1 FEASIBILITY

Enrollment: the number of AYAs enrolled divided by the number of eligible AYAs approached (hypothesized value = 60%).

Retention the percentage of AYAs who complete baseline and follow-up questionnaires (T0, T1; hypothesized value = 60%).

Adherence: the percentage of AYAs who complete at least 75% of sessions in 8 weeks (hypothesized value = 70%); alcohol monitoring hypothesized value = 70%).

We will calculate 95% CIs for feasibility measures to determine the range of estimates that are consistent with our data. We will use one-sample negative binomial probabilities and tests of binomial proportions to compare to hypothesized values. We will summarize reasons for ineligibility and refusal and compare AYAs who drop out or do not adhere by demographic and clinical characteristics, and baseline scores of the measures (e.g., PROMIS-29, alcohol use). We will investigate differences in AYA enrollment, retention, or adherence by sociodemographic and clinical characteristics (e.g., cancer type) to identify populations for a future study.

---

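### The plan gives a 60% retention benchmark and a lower limit of 18 of 40 without saying which decides, so 19 to 23 of 40 has no defined conclusion; the limit's probability is also misstated, and it is set for 40 although the protocol enrols 50

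*Combined protocol and SAP*

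**What the plan says.** The 60% figure appears in three places.

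- Protocol, Objectives, Aim 2: "Secondary feasibility outcomes include retention (=60% complete follow-up". The equals sign is probably a greater-than-or-equal sign lost in conversion, because SAP 1.2 prints that sign.
- SAP 1.2 lists retention of at least 60% among the three feasibility measures behind the sample size.
- SAP 1.4.2.1: "Retention the percentage of AYAs who complete baseline and follow-up questionnaires (T0, T1; hypothesized value = 60"%. The analysis there is a 95% confidence interval plus "tests of binomial proportions to compare to hypothesized values".

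The only operational limit is in SAP 1.2. It starts from 40 participants and a true retention of 60%, expects at least 19 to be retained, puts the probability of 19 or fewer below 0.05, and concludes: "so if more than 21 AYAs are not retained, an efficacy study may not be feasible".

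On numbers, SAP 1.2 and 1.3 use 40 for Aim 2. The protocol gives 50 (25 per arm) in Study Population, Objectives, Research Procedures and Data Collection.

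**The concern.** A benchmark on the observed proportion and a lower-tail limit derived from that benchmark answer different questions. The first asks whether 60% was reached. The second asks whether 60% can be ruled out. In a sample of 40 the two lie well apart, and the plan does not say what to conclude between them or which takes priority.

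The purpose of this pilot is to supply feasibility data for a definitive trial. If the rule for reading retention is left open, either yardstick can be chosen after the data are seen. The limit itself also has to be right. As written, its supporting probability does not match the cut-off, and its count does not carry over to the number of participants in the protocol.

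**Working it through.** **Inputs.** Benchmark 60% (Objectives, Aim 2; SAP 1.2; SAP 1.4.2.1). Limit: more than 21 of 40 not retained (SAP 1.2). Sample size: 40 (SAP 1.2 and 1.3) or 50 (protocol). Let X be the number retained, X ~ Bin(n, p).

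**1. The plan's own probability.** P(X ≤ k) = Σ C(40, x) 0.6^x 0.4^(40−x), summed over x = 0 to k.

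- P(X ≤ 19) = 0.0744. A normal approximation (mean 24, SD √9.6 = 3.098) gives 0.0533 without and 0.0732 with continuity correction. None of these is below 0.05.
- P(X ≤ 18) = 0.0392, which is below 0.05.

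More than 21 not retained means at most 40 − 22 = 18 retained. So the cut-off reproduces as a one-sided 5% limit, but the probability printed in support of it, for 19 or fewer, does not. The text is also unclear about 19 itself: the expected minimum and the cut-off leave it unflagged, while the probability statement puts it in the unlikely region.

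**2. The gap at n = 40.** The benchmark needs 0.60 × 40 = 24. The limit flags 18 or fewer (45.0%). Between them lie 19 to 23, that is 19/40 = 47.5% to 23/40 = 57.5%.

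| True retention | Flagged, X ≤ 18 | Gap, 19–23 | Benchmark met, X ≥ 24 |
|---|---|---|---|
| 50% | 0.318 | 0.548 | 0.134 |
| 55% | 0.133 | 0.548 | 0.319 |
| 60% | 0.039 | 0.393 | 0.568 |
| 70% | 0.001 | 0.062 | 0.937 |

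If 19 is counted as flagged, the gap is 20 to 23, with probability 0.43, 0.47 and 0.36 at a true 50%, 55% and 60%.

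**3. What the data would show in the gap.** The exact 95% interval is 31.5% to 63.9% at 19/40 and 40.9% to 73.0% at 23/40. Both contain 60%. At 18/40, which is flagged, the two-sided interval is 29.3% to 61.5% and still contains 60%. The one-sided limit and the planned interval therefore need not agree at the edge.

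**4. The same rule at n = 50.** The benchmark needs 0.60 × 50 = 30.

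- Literal count: more than 21 not retained means 28 or fewer retained. P(X ≤ 28 | 0.6) = 0.330. Only 29 is left in the gap.
- Re-derived one-sided 5% limit: P(X ≤ 23) = 0.0314 and P(X ≤ 24) = 0.0573, so the limit is 23 or fewer. The gap is 24 to 29, with probability 0.439 − 0.031 = 0.41 at a true 60%.

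**The case against.** A target and a one-sided test of that target can coexist, and much of this objection stands.

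A reader might infer that the protocol and the SAP give opposite answers. They do not: SAP 1.2 and 1.4.2.1 carry the same 60%, and the limit is derived from it. The gap lies within the SAP as much as between the two parts.

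A reader might also infer that the SAP passes anything it does not flag, and so passes a true retention of 50% in 68% of trials (1 − 0.318). The documents do not support that either. SAP 1.2 says only when a later trial is in doubt, in soft wording. It never says that an unflagged result is adequate or that not rejecting 60% amounts to reaching it. Nor does any section say that an observed value below 60% counts as failure. Reading Aim 2 as a cut-off on the observed proportion is natural, but it is not written.

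Retention is a secondary feasibility outcome; enrollment is primary. The 95% interval is already planned, and in the gap it would show that 60% is not excluded.

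What the objection does not remove is the absence of a stated conclusion for the gap, the incorrect probability, or the dependence of the count on n = 40. An interval describes uncertainty; it does not say how the result is to be classified.

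**Conclusion.** The point holds as a gap in the decision rule together with a misstated limit. It is not a contradiction between protocol and SAP. At n = 40, 19 to 23 retained has no defined conclusion, and this is a likely result: about 4 in 10 trials when true retention is exactly 60%, and more than half at 50% or 55%. The supporting probability is 0.074 where the SAP says below 0.05. Applied literally to 50 participants, the limit would flag a true 60% in 33% of trials, against 3.9% at 40.

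These figures assume independent participants with a common retention probability, as the SAP's own calculation does. The width of the gap depends on the sample size used: 19 to 23 of 40, or 24 to 29 of 50 if the limit is re-derived. Since retention is secondary and the limit is softly worded, this calls for clarification and does not put the design in doubt.

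**What to change.** In SAP 1.2:

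1. Correct the probability statement from 19 or fewer to 18 or fewer (0.039 at n = 40).
2. Recompute the limit for the number of participants actually used, once 40 and 50 are reconciled. At 50, the one-sided 5% limit is 23 or fewer retained.
3. State one three-way reading and refer to it from SAP 1.4.2.1 and Aim 2:
   - observed retention at least 60%: benchmark met;
   - 60% excluded by the one-sided 5% test: an efficacy study may not be feasible as designed;
   - in between: benchmark not met and 60% not excluded, reported with the planned 95% interval and not called feasible.

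Say that the one-sided test sets the lower boundary, because the two-sided interval can still contain 60% there.

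The cost is wording only, with no new data or participants. The downside is a less favourable feasibility statement in the middle band, which occurs in about 4 in 10 trials even at a true 60% (39% at n = 40, 41% at n = 50).
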